## Duration of overall response

 The duration of overall response is measured from the time measurement criteria are met for CR or PR (whichever status is recorded first) until the first date that recurrence or PD is objectively documented, taking as reference for PD the smallest measurements recorded since the treatment started.

### Duration of stable disease

- SD is measured from the start of the treatment until the criteria for disease progression are met, taking as reference the smallest measurements recorded since the treatment started.
- The clinical relevance of the duration of SD varies for different tumour types and grades. Therefore, it is highly recommended that the protocol specify the minimal time interval required between two measurements for determination of SD. This time interval should take into account the expected clinical benefit that such a status may bring to the population under study.

## Response review

 For trials where the response rate is the primary endpoint it is strongly recommended that all responses be reviewed by an expert(s) independent of the study at the study's completion. Simultaneous review of the patients' files and radiological images is the best approach.

# Reporting of results

- All patients included in the study must be assessed for response to treatment, even
  if there are major protocol treatment deviations or if they are ineligible. Each patient
  will be assigned one of the following categories: 1) complete response, 2) partial
  response, 3) stable disease, 4) progressive disease, 5) Non-evaluable for response:
  specify reasons (early death, malignant disease; early death, toxicity; tumour
  assessments not repeated/incomplete; other (specify))
- All of the patients who met the eligibility criteria should be included in the main analysis of the response rate. Patients in response categories 4-9 should be considered as failing to respond to treatment (disease progression). Thus, an incorrect treatment schedule or drug administration does not result in exclusion from the analysis of the response rate. Precise definitions for categories 4-9 will be protocol specific.
- All conclusions should be based on all eligible patients.
- Sub-analyses may then be performed on the basis of a subset of patients, excluding
  those for whom major protocol deviations have been identified (e.g., early death due
  to other reasons, early discontinuation of treatment, major protocol violations, etc.).
  However, these sub-analyses may not serve as the basis for drawing conclusions
  concerning treatment efficacy, and the reasons for excluding patients from the
  analysis should be clearly reported.
- The 95% confidence intervals should be provided

# APPENDIX 2: CLINICAL AND COMPOSITE RESPONSE CRITERIA FOR PATIENTS WITH ABCC

These criteria are designed for externally visible lesions that can be measured bidimensionally using digital medical photography. This appendix also provides clinical and composite response criteria for disease that is measureable by both clinical response criteria and RECIST 1.1.

Patients will be followed by digital medical photography and also undergo radiologic imaging (MRI/CT scan) at baseline, and this will also be performed serially at each response assessment unless the investigator deems that baseline radiologic imaging was uninformative. Radiologic imaging will be essential in the evaluation of tumours that have subdermal components that cannot be adequately assessed by digital medical photography. Standardised digital photographs of the externally visible component of all target lesions must be obtained at baseline and at the time of each subsequent tumour assessment. Investigators will also provide a clinical description of the externally visible target lesion(s) at baseline and at each tumour assessment, as well as comments on any changes in the lesion(s) since the previous assessment.

For target lesions that are measured by digital medical photography, measurements will be bi-dimensional.

### SPECIAL ISSUES FOR EXTERNALLY VISIBLE TUMOURS:

# 1) Anatomic Defects

Regarding tumour around a surgical cavity/anatomic defect (e.g. rhinectomey), such lesions should be considered non-measureable unless there is a nodular lesion measuring ≥10 mm in maximal bidimensional perpendicular diameters. The surgical cavity or anatomic defect should not be considered in measuring the lesion.

## 2) Indeterminate-Appearing Tissue

If there is uncertainty about whether a given lesion or area of a lesion represents malignancy versus benign process (e.g. scarring, fibrosis), biopsies should be obtained. Indeterminate-appearing areas (e.g. scarring, fibrosis) are included in the tumour measurements unless biopsies are obtained to establish benign status.

**Note on timeline for finalisation of measurement/response assessment:** Generally, baseline disease measurements and response assessments should be completed on the day of the visit at which digital medical photography was performed.

When biopsies are performed to confirm pCR, the annotated photograph for that visit should clearly indicate the region of the tumour that was biopsied. It is not necessary to hold study treatment while the local pathology report is pending.

# 3) Central Review

An independent central review, with access to de-identified digital medical photography results and biopsy results, will provide response assessments to address study objectives. Central reviews will not be continuous or "real-time." Clinical management decisions generally will be as per investigator response assessments and local pathology review. In the unlikely event that central review yields major differences with the local response assessment that could have implications for the ongoing management of an active patient

on study; the situation will be discussed between the sponsor and the investigator in order to determine patient management.

# 4) Confirmation of Responses

For any complete responses observed in digital medical photography of externally visible target lesions, confirmatory biopsies are required to establish status of complete response.

# 5) Patients with Deeply Invasive Tumours

Tumour measurements for these patients will generally be performed with digital medical photography (bi-dimensional measurements). However, some patients may have deeply invasive target lesions in which tumour measurements can better be obtained with cross-sectional imaging (MRI/CT scans). For any target lesions that are measured by cross-sectional imaging, measurements will be unidimensional according to RECIST 1.1.

# **Clinical Response Criteria for Externally Visible Tumours**

# A. Externally Visible Tumour Dimension

The externally visible component of target lesion(s) will be measured using bi-dimensional WHO criteria as the sum of the products (of individual target lesions) in the longest dimension and perpendicular second longest dimension – at each tumour assessment and will be documented using standardised digital photography. In the absence of substantial change in lesion geometry, subsequent visit measurements should be performed in the same axes and the investigator should refer to the previous visit's annotated photographs as a starting point to identify axis for measurement when making subsequent assessments.

Clinical response criteria for externally visible tumour(s) require bi-dimensional measurements according to WHO criteria, and are as follows:

- Complete response of externally visible disease (vCR): all target lesion(s) and non-target lesions no longer visible, maintained for at least 4 weeks. Documentation of vCR requires confirmation by biopsies of site(s) of externally visible target lesion(s) with histologic confirmation of no residual malignancy. In the absence of such histologic confirmation, a patient cannot be deemed to have experienced vCR and the best response would be partial response.
- Partial response of externally visible disease (vPR): decrease of 50% (WHO criteria) or greater in the sum the products of perpendicular longest dimensions of target lesion(s), maintained for at least 4 weeks
- Stable externally visible disease (vSD): not meeting criteria for vCR, vPR, or progressive disease
- Progression of visible disease (vPD): increase of ≥25% (WHO criteria) in the sum of the products of perpendicular longest dimensions of target lesion(s). In rare cases, unequivocal progression of a non-target lesion may be accepted as vPD.

# **B. New Lesions**

A new cutaneous lesion consistent with BCC will be considered as cPD if the lesion is ≥10 mm in both maximal perpendicular diameters and can be clearly documented as not being previously present, unless it is confirmed on biopsy not to be consistent with BCC. If a new cutaneous lesion is not biopsied or if the histology is inconclusive, it should be considered BCC and deemed cPD.

TABLE 1: Overall Clinical Responses For Advanced BCC Lesions that are Measured by Digital Medical Photography

Externally Visible Tumour Dimension a	New Lesions a	Clinical Response
vCR	No	cCR b,c
vPR	No	cPR d
vSD	No	cSD e
vPD	Yes or No	cPD f
Any	Yes	cPD+

- a See above for definitions
- b Clinical Complete Response
- c Negative biopsy showing no residual malignant cells is required for any lesion be deemed cCR
- d Clinical Partial Response
- e Clinical Stable Disease
- f Clinical Progression of Disease

# **Composite Response Criteria**

For patients with advanced BCC that is measurable by BOTH clinical response criteria by digital medical photography and RECIST 1.1 using radiologic imaging. The "Clinical Response" column in this table will be based on the results of the "Clinical Response" (far right) column of the table above. A Central Review of the results from independently evaluated radiological scans, photographs and clinical tumour biopsies (if performed) to derive overall composite responses.

In addition, if all previously inoperable target lesions are rendered operable with clear margins obtained at the time of surgery, this will be considered a PR. If the investigator deems a previously unresectable lesion to be potentially resectable due to response to cemiplimab, the CI should be consulted prior to any surgical procedure being performed.

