#### 4.3 Inclusion Criteria

- 1. Signed informed consent
- 2. Men and women age ≥ 18 years
- ECOG performance status 0 or 1
- 4. Histologically confirmed disease (from diagnostic biopsy) that is considered to be inappropriate for surgery (see below), in the opinion of a Super Specialist-MDT (SS-MDT) reason must be fully documented:

Acceptable inoperable / medical contraindications to surgery include:

- a. BCC that has recurred in the same location after two or more surgical procedures and curative resection is deemed unlikely
- b. BCC ≥10 mm, and relapsing after 2 surgeries in critical locations (e.g. periocular and perioral areas)
- c. BCC infiltrating in bone/cartilage/other structures or with significant local invasion and curative resection is unlikely

- d. Relapsing BCC after multiple surgeries and/or radiotherapy
- e. BCC in patients whose co-morbidities preclude them from general anaesthesia/surgery.
- f. BCC in anatomically challenging locations/size for which surgery may result in substantial morbidity and/or deformity (e.g. removal of all or part of a facial structure, such as nose, ear, eyelid, eye; or requirement for limb amputation); or patient's reluctance to accept the consequences of surgery.
- 5. Patients must be deemed as inappropriate for radiotherapy in the opinion of a SS-MDT. Specifically, patients must meet at least 1 of the following criteria (reason must be fully documented):
  - a. A patient previously received radiotherapy for BCC, such that further radiotherapy would exceed the threshold of acceptable cumulative dose, as per the clinical oncologist.
  - b. Judgment of clinical oncologist that such tumour is unlikely to be curative or radiotherapy was deemed to be contraindicated.

Acceptable contraindications to radiotherapy for patients who have not received any prior radiation include:

- a. laBCCs in anatomically challenging locations for which radiotherapy would be associated with unacceptable toxicity risk in the context of the patient's overall medical condition in the opinion of the multidisciplinary team.
- b. Radiotherapy is contraindicated or inappropriate (limitations because of location of tumour, or cumulative prior radiotherapy dose).

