#### 9.1 Permanent treatment discontinuation from the IMP

Permanent treatment discontinuation is any treatment discontinuation associated with the definitive decision from the investigator or the patient not to re-expose the patient to the IMP at any time.

If a patient shows one of the following reasons, the study treatment must be discontinued:

- Progression of basal cell carcinoma as per clinical response criteria/RECIST 1.1/composite response criteria (unless continuation of cemiplimab is deemed to be of clinical benefit e.g. it is within the first 12 weeks of treatment (scan 1) and thought to be pseudo-progression, in which case it should be discussed with the CI or nominated representative).
- Unacceptable toxicity or adverse event requiring discontinuation of treatment
- Patient requests to stop treatment including if they change their mind about wanting curative surgery e.g. if the surgery is curative but potentially disfiguring
- Patient shows non-compliance (including persistent patient attendance failure).

The patients may withdraw from treatment with IMP at any time and irrespective of the reason, or this may be the investigator's decision. The reason for treatment discontinuation will be documented as far as possible on the appropriate eCRF.

Further medical or surgical treatment following trial immunotherapy is at the discretion of the treating clinician in consultation with the patient.

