### **Documentation of New Lesions**

 The presence of a new lesion should be unequivocal: i.e. not attributable to differences in scanning technique, change in imaging modality or findings thought to represent something other than tumour (for example, some 'new' bone lesions may be simply healing or flare of pre-existing lesions). • A lesion identified at a follow-up visit in an anatomical location that was not scanned at baseline is considered a new lesion and will indicate disease progression.

Response Criteria	Evaluation of target lesions
* Complete Response (CR):	Disappearance of all target lesions. Pathological lymph nodes (whether target or non-target) must have reduction in short axis to <10mm.
* Partial Response (PR):	At least a 30% decrease in the sum of the LD of target lesions, taking as reference the baseline sum LD
* Progressive Disease (PD):	At least a 20% increase in the sum of the LD of target lesions, taking as reference the smallest sum LD recorded since the treatment started or the appearance of one or more new lesions. In addition, the smallest sum LD must also demonstrate an absolute increase of at least 5mm.
* Stable Disease (SD):	Neither sufficient shrinkage to qualify for PR nor sufficient increase to qualify for PD, taking as reference the smallest sum LD since the treatment started
	Evaluation of non-target lesions
* Complete Response (CR):	Disappearance of all non-target lesions and normalization of tumour marker level
*Non-CR/non-PD:	Persistence of one or more non-target lesion(s) or/and maintenance of tumour marker level above the normal limits
* Progressive Disease (PD):	Unequivocal progression of existing non- target lesions (1). The appearance of one or more new lesions is also considered progression.

 Although a clear progression of "non target" lesions only is exceptional, in such circumstances, the opinion of the treating physician should prevail and the progression status should be confirmed later on by the review panel (or study chair).

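### Appendix 2 lets a clear-margin resection be scored as a partial response without measured shrinkage, so a patient with stable disease who later accepts surgery can be counted as a cemiplimab responder

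*Protocol*

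**What the plan says.** The protocol defines the primary endpoint as the proportion with CR or PR at 6 months by independent central review (sections 2.2 and 11.3). The ordinary routes to PR are measured:

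- Photography (Appendix 2, part A): "decrease of 50% (WHO criteria) or greater in the sum the products of perpendicular longest dimensions of target lesion(s), maintained for at least 4 weeks".
- Imaging (Appendix 1): "At least a 30% decrease in the sum of the LD of target lesions".

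After introducing the composite criteria, Appendix 2 adds another route: "if all previously inoperable target lesions are rendered operable with clear margins obtained at the time of surgery, this will be considered a PR". The next sentence deals with a lesion that the investigator considers "potentially resectable due to response to cemiplimab, the CI should be consulted prior to any surgical procedure being performed".

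Section 4.3, criterion 4, gives its list of reasons under the heading "Acceptable inoperable / medical contraindications to surgery include". Item 4f covers sites or sizes where surgery would cause substantial morbidity or deformity, and ends with "or patient's reluctance to accept the consequences of surgery". Section 9.1 lists among the reasons for stopping treatment: "Patient requests to stop treatment including if they change their mind about wanting curative surgery".

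**The concern.** The surgical route has no size threshold, no maintenance period and no required assessment before the operation. Nor does it say that the lesion must have become operable because the tumour responded. Inoperable is not a fixed property of the tumour in this trial, because 4f puts a patient's reluctance under that label.

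Take a 4f patient with stable disease at week 12 who then accepts surgery and has clear margins. Table 2 of Appendix 2 would give stable disease. The added sentence can be read to give PR, although the only thing that changed was the patient's decision.

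The trial is single-arm and asks what cemiplimab alone achieves. A surgical success credited to the drug moves ORR in one direction only, and it enters both the interim decision at 18 patients and the primary result.

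**Working it through.** **Is the consequence blocked anywhere?**

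- *Appendix 2, Composite Response Criteria.* The reference to response to cemiplimab stands in the sentence that triggers a consultation with the Chief Investigator. It is not a condition for scoring PR.
- *Trial Summary, main exclusion criteria.* Candidates for curative surgery are excluded there. The item is missing from the list in section 4.4, and it sits uneasily with 4f and section 9.1.
- *Section 11.6.* A patient who leaves the trial by preference can be non-evaluable and replaced, but only if disease cannot be measured after treatment. Sections 9.1.1 and 9.2 keep patients who merely stop treatment in follow-up, and a week-12 assessment may already exist.
- *Sections 2.2 and 11.3, and Table 2.* None of them mentions the surgical route.

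The same patient could thus be PR, stable disease or non-evaluable, depending on which section is applied.

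**The plan's own design (section 11.1).** Poor rate 25%, good rate 45%, alpha 5%, power 80%; 18 patients in stage 1, continue at 6 or more responders; 19 more patients, 37 in total. The final cut-off r is not printed, so I searched for it with the exact two-stage binomial:

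P(success | p) = Σ over x = 6 to 18 of P(X1 = x) × P(X2 ≥ r − x), with X1 ~ Bin(18, p) and X2 ~ Bin(19, p).

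| r | Type I error (p = 0.25) | Power (p = 0.45) |
|---|---|---|
| 13 | 0.0876 | 0.852 |
| 14 | 0.0496 | 0.806 |
| 15 | 0.0249 | 0.732 |

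Of these, only r = 14 meets 5% and 80%, so it is used below. Stopping early at 15 of 18 does not change these figures to four decimals.

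**Effect of surgery-derived PRs.** Let k be the average number of patients in 37 who have no measured response but are scored PR through surgery. The documents give no value for k, so the range is an assumption. Under the poor rate the apparent response rate is p = 0.25 + k/37; for k = 1 this is 0.25 + 0.027 = 0.277.

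| k (assumed) | Apparent rate | Type I error | P(pass stage 1) = P(X1 ≥ 6) |
|---|---|---|---|
| 0 | 0.250 | 0.050 | 0.28 |
| 0.25 | 0.257 | 0.060 | 0.31 |
| 0.5 | 0.264 | 0.073 | 0.33 |
| 1 | 0.277 | 0.10 | 0.38 |
| 2 | 0.304 | 0.18 | 0.48 |
| 3 | 0.331 | 0.29 | 0.58 |

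Each such patient adds 1/37 = 2.7 percentage points to ORR. The design has almost no spare alpha (0.0496 against 0.05), so an average of one roughly doubles the error.

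**The case against.** The best defence is the wording itself. A lesion that is rendered operable is one that has changed, and the following sentence names response to cemiplimab as the cause. Section 9.1 treats a change of mind separately, as a reason to stop treatment, and a tumour that could have been resected all along was not rendered operable. This is probably what the authors meant. It does not close the gap, because the intended cause is not a scoring condition and 4f itself labels reluctance cases inoperable. Central review sees photographs, scans and biopsies, none of which show why a patient accepted surgery.

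Three further objections stand in part:

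- *Few patients may be affected.* Criterion 4 needs a documented opinion of the specialist multidisciplinary team, and criterion 5 needs unsuitability for radiotherapy. Resection of every target lesion with clear margins must also fall within 6 months. Values of k below one are therefore plausible and are shown.
- *Reach is unclear.* The sentence sits under criteria for patients measurable by both methods. Whether it extends to photography-only or imaging-only patients is not stated, while the calculation applies it to all 37.
- *Requiring a confirmed PR before surgery would err the other way.* Assessments are 12 weeks apart (section 6.5.1). A patient who reached the threshold at week 12 and was operated on before week 24 would have no scheduled confirming assessment.

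A reader might also infer that PFS and every durability endpoint are inflated. The protocol does not support this. PFS does not use PR status (sections 2.3 and 11.4). Section 2.3 dates response by shrinkage of at least 30%, so it is not established that a PR without shrinkage enters duration of response. New lesions still count as progression after a resection.

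**Conclusion.** The point holds as an ambiguity that can bias the primary endpoint upward. As written, a clear-margin resection can be scored PR without measured shrinkage, and nothing prevents this for a patient enrolled on reluctance who later accepts surgery. It would go too far to say that the protocol intends a change of mind to count as a response, or that it always will.

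The size depends on two assumptions: a final cut-off of 14 of 37, and the number of affected patients. For an average of 0.25 to 3 such patients in 37, the type I error rises from 5.0% to between about 6% and 29%. The documents do not show where in that range the trial would fall. The Trial Summary exclusions, criterion 4f, sections 9.1 and 11.6, and Appendix 2 must be reconciled. No view is taken here on when surgery should be offered.

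**What to change.** In Appendix 2 and sections 2.2 and 11.3:

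1. Count an operated patient as a responder in the primary ORR only if the measured PR or CR threshold (clinical, RECIST 1.1 or composite) was met at the last central assessment before surgery. Treat the 4-week maintenance requirement as satisfied where surgery came before a confirming assessment was due.
2. Report conversion to operable with clear margins as a separate outcome, by inclusion reason 4a to 4f.
3. Add a sensitivity analysis of ORR that counts these patients as PR.
4. State whether the surgical rule covers composite patients only or all patients, and align the sections named in the verdict.

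A rule to censor PFS at surgery is not needed for this point.

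The cost is wording and a little analysis. Photographs are already scheduled every 12 weeks, imaging too where it is used to follow target lesions, and further treatment for the disease is recorded (section 7.4). The downside is that ORR may be slightly lower, because a patient whose tumour truly became operable below the PR threshold appears only in the separate outcome and the sensitivity analysis.
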